13.9 VA SENSITIVE DATA (VASI)

13.10 Please describe your use of VA Sensitive Information (VASI):

- This protocol does not collect or use VASI
- This protocol uses, but does not save, collect, copy, or record VASI.
- This protocol collects, records, or saves VASI.

In which of the following ways will VASI be accessed/collected?

- Computer access
- Medical chart review
- Patient treatment
- Personal interviews
- Other

Please give a brief description of the data sources mentioned above and how they will be accessed.

Medical charts will be used to identify patients who meet study eligibility criteria and also to order and record laboratory tests (i.e., HbA1c, lipid panel). Study participants will be invited to take part in optional semi-structured interviews at 6 and 12 months. Participants will complete surveys at baseline, 6 months, and 12 months; these surveys will include self-reported side effects and experiences with the intervention.

13.11 Indicate the type of PII to be accessed. If you requested a HIPAA waiver for screening only, indicate any additional PII types that will be used post-screening.

- Names
- Any geographic area smaller than a state
- Any date (except year) that is directly related to an individual and/or ages over 89
- Telephone numbers
- Fax numbers
- Email addresses
- Social Security Numbers (SSNs) or Scrambled SSNs
- Medical record numbers
- Health plan beneficiary numbers
- Account numbers
- Certificate and/or license numbers
- Vehicle ID and serial numbers including license plate numbers
- Device identifiers and serial numbers
- Web Universal Resource Locators (URLs)
- Internet protocol (IP) addresses
- Biometric identifiers, including finger & voice prints
- Full-face photographic images and any comparable images
- Any other unique identifiers (number, characteristic, or code)
- None of the above

Please explain the other unique identifier(s).

Other identifier is CDW PatientICN. Biometric identifiers refer to voice recordings collected during interviews.

13.12 Will this protocol include the use of Protected Health Information (PHI) that requires specific consent from subjects? If you requested a HIPAA waiver for screening only, indicate any PHI types that will be used post-screening.

- Alcoholism or alcohol abuse information
- Drug abuse information
- Sickle cell anemia information
- HIV test/infection results
- None of the above

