We will recruit up to 30 veterans with prediabetes to participate in the LC-DPP. The intervention will be delivered in partnership with VA Certified Diabetes Educators who will serve as lifestyle coaches for the group-based intervention. The LC-DPP lifestyle coaches will deliver 16-weekly one-hour group sessions over the first 6 months and 8 maintenance sessions over the subsequent 6 months. **Table 1** shows session topics. Participants will receive a binder to hold study materials. They will be provided with printed handouts on a session-by-session basis. Individuals that are absent for a particular session will receive corresponding session materials by e-mail or postal mail.

The CDC's Diabetes Prevention Program instructs participants to adhere to a fat-restricted diet with an explicit cap of less than 33-55 grams of fat per day depending on starting body weight. In contrast, LC-DPP participants will be initially instructed to follow *ad-libitum* very low-carbohydrate diet, which restricts carbohydrate intake (not including fiber) to 20-35 grams per day with the goal of achieving nutritional ketosis. Participants will be encouraged to eat a normal amount of protein (roughly 80-120 grams per day) and to derive the remaining calories from fat. Allowable foods include: meats, fish, poultry, eggs, cheese, seeds, nuts, leafy greens, non-starchy vegetables, and some fruits.

During the LC-DPP's maintenance phase, participants will be instructed to gradually reintroduce carbohydrates (e.g., 5 non-fiber grams of carbohydrates per week) if: (1) they have met their weight loss target and (2) if they desire to liberalize their carbohydrate intake.

To minimize potential side effects (e.g. headache, constipation, muscle cramps, diarrhea, general weakness, and rash) participants will be instructed to replace one meal a week with a low-carbohydrate alternative, starting with breakfast. Participants will be counseled to drink sufficient water and to consume adequate sodium. Further, primary care providers will be notified of their patients' involvement in this study, and they will be given a handout that describes the intervention, potential side effects, and strategies to minimize side effects.

Session Number	Topic
Core phase	
0	Study information session (Informed consent to be obtained)
1	Welcome to the Low-Carb Diabetes Prevention Program
2	Be a Carbohydrate Detective
3	Low-Carb Meals
4	Low-Carb Cooking and Shopping
5	Move Those Muscles

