5.5 Study Evaluations

Quantitative Data source

a) Weight

Participants will be encouraged to self-monitor weight using a home scale although this

data will not be collected by the study team. In accordance with standard DPP operating procedure, participants will be weighed in a private room prior to each session and their weight will be recorded by a member of the study team.

b) Physical activity

In accordance with standard DPP operating procedure, participants will be encouraged to self-monitor physical activity minutes and to report this information to the lifestyle coach at the start of each session.

c) Laboratory metrics

We will evaluate change in A1c and lipids over the study period. Baseline laboratory studies will be obtained once individuals have consented to participate in this study. Repeat A1c and lipid levels will be drawn at 6 and 12 months.

d) Session attendance

Participants will be encouraged to attend all sessions and attendance will be recorded by the lifestyle coach.

e) Survey Data

At baseline, 6 months, and 12 months, study participants will be invited to complete a written survey. Paper copies will be given to individuals at session 15/16. Because we aim to obtain complete follow-up data, we will make efforts to collect survey responses from participants that are not present for session 15/16. We will send surveys to non-attendeess via postal mail. All individuals will be asked to return their survey to the study team via pre-paid envelope or in-person delivery. The survey will assess domains related to the following: global health and well-being; sleep; food cravings; stress eating; hunger; energy; mood; physical symptoms, neuropathic symptoms (e.g., tingling, burning in feet); side effects; and cost of food. At baseline, we will ask participants to provide sociodemographic characteristics. At 6 months and 12 months, participants will be asked to provide feedback about the study and will receive compensation for each survey.

Qualitative Data Sources

Participants will be encouraged to maintain a log of food intake and physical activity. Each week, the lifestyle coach will review the logs and provide individual feedback. We will retain copies of participants' logs from their first 2 weeks in the study and their last 2 weeks in the study. In this way, we can qualitatively assess changes in dietary habits and physical activity.

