Change in body weight: Body weight will be measured and recorded at each attended session. We will calculate average body weight change and percent body weight loss at the end of the program's core phase (6 months) and maintenance phase (12 months). Among session non-attendees, we will attempt to schedule 6- and 12-month weigh-ins at participants' convenience within 2 weeks of the final core and maintenance sessions. All weights will be obtained using the same calibrated scale.

Change in HbA1c: We will calculate change in HbA1c from baseline to 6 and 12 months

Change in lipids: We will calculate change in triglycerides and total cholesterol/HDL ratio from baseline to 6 months and 12 months.

Change in survey measures: We will calculate change in self-reported survey measures from baseline to 6 months and 12 months.

Fidelity: We will measure intervention fidelity (i.e., extent to which components of an intervention are delivered as intended) using quantitative measures adapted from the literature²⁶ as well as qualitative interview feedback from participants and dietitians.

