5.6 Data Analysis

Quantitative analysis

Descriptive statistics will be used for baseline survey response data including demographic and socioeconomic characteristics. For all continuous outcomes, we will calculate mean change and standard deviation from baseline to 6 months and 12 months and compare outcomes from baseline to 6 months and 12 months using paired *t*-tests. For all categorical outcomes, we will

use chi-square or Fisher's exact tests to examine changes from baseline to 6 and 12 months. All analyses will be conducted using Stata 14.

Qualitative analysis:

Semi-structured interviews will be recorded and transcribed verbatim. Interviews will then be imported into qualitative analysis software. Two investigators will independently read and code transcribed interviews. Interviews will then be coded jointly using consensus conferences. Interviews will be analyzed using directed content analysis²⁷, which is to say that codes will be created to reflect the main topics in the interview guide and to characterize the patterns and themes that emerged from the data.²⁸

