Low-Carbohydrate Diabetes
Prevention Program Among
Veterans With Prediabetes (VA LC-
DPP)

Prepared for ClinicalTrials
Resubmission 4/20/21

Statistical Analysis Plan:

Quantitative analysis

Descriptive statistics will be used for baseline survey response data including demographic and socioeconomic characteristics. For all continuous outcomes, we will calculate mean change and standard deviation from baseline to 6 months and 12 months and compare outcomes from baseline to 6 months and 12 months using paired t-tests. For all categorical outcomes, we will use chi-square or Fisher's exact tests to examine changes from baseline to 6 and 12 months. All analyses will be conducted using Stata 14.

Qualitative analysis:

Semi-structured interviews will be recorded and transcribed verbatim. Interviews will then be imported into qualitative analysis software. Two investigators will independently read and code transcribed interviews. Interviews will then be coded jointly using consensus conferences. Interviews will be analyzed using directed content analysis²⁷, which is to say that codes will be created to reflect the main topics in the interview guide and to characterize the patterns and themes that emerged from the data.²⁸

**Cravings:
Control of Eating Questionnaire**

Over the past 7 days...

How strong was your desire to eat sweet foods?	Q1	Answer choices on a sliding scale from 0 to 100 with anchors at 0 and 100:	Items on the CoEQ are assessed by 100 mm VAS with items relating to each subscale being averaged to create	Dalton M, Finlayson G, Hill A, Blundell J. Preliminary validation and principal components analysis of the Control of
How strong was your desire for non-	Q2	0- not at all strong 10 20	to create	

Over the past 7 days, how often have you had cravings for

Sweet foods like	Q3	Answer choices	
Other sweet foods (cakes, pastries, cookies, etc)?	Q4	on a sliding scale from 0 to 100 with anchors at 0 and 100:	
Fruit or fruit juice?	Q5	0- not at all	
Dairy foods (cheese, yogurts, milk, etc)?	Q6	10 20 30 40 50 60 70 80 90 100-	
Starchy Foods that are not sweet like French fries, potato chips,	Q7 Q8	70 80 90 100- extremely often	

Stress Eating

Please indicate how you usually experience a stressful event

I eat more of my favorite foods to	Q1	Answer choices 1 through 4 with anchors on 1 and 4:	Reverse code and sum, so that higher scores indicated	Tsenkova, V., Boylan, J. M., & Ryff, C. (2013). Stress
------------------------------------	----	---	---	--

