Below is a list of reasons that people sometimes give for eating tasty foods and drinks such as:

- Sweets like chocolate, doughnuts, cookies, cake, candy, ice cream, other desserts.
- Salty snacks like chips, pretzels, and crackers.
- Fast foods like hamburgers, cheeseburgers, pizza, fried chicken and French fries.
- Sugary drinks like soda, sweet tea, milkshakes, and smoothies.

To forget y	Q3	1 =	Coping	Burgess,
Because it	Q4	Almost	score:	E. E.,
To cheer u	Q5	never/Ne	Average	Turan, B.,
To forget a	Q6	ver	of four	Lokken, K.
		2 = Some	responses	L., Morse,
		of the	.	A.. &

Energy Levels between Meals

In the past week, two hours after you ate BREAKFAST, how do you feel?

Alert	Q1	Answer	NA	NA
Energetic	Q2	choices 1		
Tired	Q3	through		
Brain fog o	Q4	7, with		
Food cravii	Q5	anchors		
Hunger	Q6	on 1, 7:		
Moodiness	Q7	1- Not at		
		all		
		7		

In the past week, two hours after you ate LUNCH, how do you feel?

Alert	Q8	Answer	NA	NA
Energetic	Q9	choices 1		
Tired	Q10	through		
Brain fod o	Q11	7, with		
Food cravii	Q12	anchors		
Hunger	Q13	on 1, 7:		
Moodiness	Q14	1- Not at		
		all		

Physical Symptoms

How often have you experienced the following over the past week?

Acne	Q1		NA	NA
Bad breath	Q2			
Bloating or	Q3			

Cold hands Q4
Constipation Q5
Diarrhea Q6
Dizziness Q7
Dry mouth Q8
Constant tiredness Q9
Food intolerance Q10

Headaches Q11

Heart palpitations or a racing heart Q12

Heartburn Q13

Joint or muscle pain Q14

Muscle cramps Q15

Nausea Q16

Trouble concentrating Q17

Weakness Q18

Hair loss Q19

Sexual problems Q20

Numbness (loss of sensation) in the feet, legs, or hands Q21

Tingling or prickling sensation in the feet, legs, or hands Q22

Not at all
1 day a week
2-3 days a week
4-5 days a week
6-7 days a week

Burning or shooting pain in the feet, legs, or hands

Q23

Blurred or deteriorating vision

Q24

Please describe any other psychological or physical symptoms that you experienced during the past month.

Q25

Participants may enter free text of whatever they choose.

Health
Global Health PROMIS Questionnaire:

Please respond to each item by marking one box per row

In	Q1	5-	Re-code:	PROMIS
In	Q2	Excellent	Q7 (pain	Health
general,		4- Very	on	Organizati
would		good	average):	on and
you say		3- Good	0 = 5	PROMIS
your		2- Fair	1,2,3 = 4	Cooperati
quality of		1- Poor	4,5,6 = 3	ve Group,
life is:			7,8,9 = 2	2008-
In	Q3		10 = 1	2012.
general,				https://w
how			Global	ww.iconq
would			Physical	uerms.org
you rate			Health	/sites/all/

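### The symptom checklist is analysed only as change from baseline, which nets new against resolved symptoms; no count of participants with a new or worsened symptom is promised

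*Protocol*

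**What the plan says.** Protocol 5.5 (Survey Data) lists among the survey domains "physical symptoms, neuropathic symptoms (e.g., tingling, burning in feet); side effects; and cost of food". Section 13.10 of the IRB application says "these surveys will include self-reported side effects and experiences with the intervention". Surveys are given at baseline, 6 months and 12 months.

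The SAP's survey table contains a Physical Symptoms block, headed "How often have you experienced the following over the past week". It has 24 rated symptoms and one free-text item. Each rated symptom takes one of five frequencies, from 'Not at all' to '6-7 days a week'. The scoring entry is NA.

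The only analysis rule that reaches this block is in Protocol 5.5, Secondary Measures: "We will calculate change in self-reported survey measures from baseline to 6 months and 12 months". For continuous outcomes the SAP states "we will calculate mean change and standard deviation from baseline to 6 months and 12 months", with paired t-tests. For categorical outcomes it states "we will use chi-square or Fisher's exact tests to examine changes from baseline to 6 and 12 months". Protocol 5.6 has the same text. Descriptive statistics are promised for baseline only: "Descriptive statistics will be used for baseline survey response data including demographic and socioeconomic characteristics".

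The expected side effects are named in Protocol 5.1. The Intervention text begins "To minimize potential side effects (e.g. headache, constipation, muscle cramps, diarrhea, general weakness, and rash", and the Risks and Benefits text adds bad breath.

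**The concern.** A mean change, or a comparison of prevalence at two times, is a net figure. A participant who becomes constipated is offset by one whose constipation resolves. For a weight or an A1c that is the intended summary. For a harm it leaves out the number a reader wants, which is how many people acquired or worsened in the symptom.

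Followed as written, the pilot could report no change in constipation or headache while some participants newly have it. Acceptability is a primary outcome, Protocol 5.5 names side effects as a possible barrier to adherence, and the abstract says the data will inform a larger comparative trial. In my judgement a count of people with a new or worse symptom serves those purposes better than a mean change; the documents do not themselves state that need.

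**Working it through.** The documents state no symptom rate and no figure for this point, so there is nothing to reproduce. The check has four steps.

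**1. Coverage.** Protocol 5.1 names seven side effects across its Intervention and Risks text: headache, constipation, muscle cramps, diarrhea, general weakness, rash and bad breath. The checklist has bad breath (Q2), constipation (Q5), diarrhea (Q6), headaches (Q11), muscle cramps (Q15) and weakness (Q18). That is six of seven; rash is absent.

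**2. Can the planned output cancel?** Inputs: n = 30 is the recruitment maximum; n = 22 is the plan's 10% enrolment applied to 220 letters (0.10 × 220). The symptom counts are my assumptions. Categories are coded 0 to 4, so '2-3 days a week' is 2.

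| Assumed case | Mean change (SD), paired t | New among 'Not at all' at baseline (exact 95% CI) |
|---|---|---|
| n = 30; 6 affected at baseline; 4 go 2→0, 4 go 0→2 | (4×2 − 4×2)/30 = 0.00 (1.05), p = 1.0 | 4/24 = 17% (4.7 to 37.4%) |
| Same, but the new cases go 0→1 | (4×1 − 4×2)/30 = −0.13 (0.82), p = 0.38 | 4/24 = 17% (4.7 to 37.4%) |
| n = 22; 4 affected at baseline; 3 go 2→0, 3 go 0→2 | (3×2 − 3×2)/22 = 0.00 (1.07), p = 1.0 | 3/18 = 17% (3.6 to 41.4%) |

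In the first case prevalence is 6/30 at both times, and Fisher's test comparing the two gives p = 1.0. Among all 30, 4 worsened and 4 improved (each 13%, CI 3.8 to 30.7%). In the second case the mean even looks favourable.

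**3. Would chi-square/Fisher help?** The layout is not stated. A baseline-by-follow-up table would show new and resolved cases in its cells, but the test on it asks whether baseline and follow-up status are associated, not whether the symptom changed. In the first case that table is [[20, 4], [4, 2]] (rows baseline absent/present, columns follow-up absent/present), with Fisher p = 0.57. In an assumed table [[12, 12], [3, 3]], prevalence rises from 6/30 to 15/30: Fisher gives p = 1.0, while exact McNemar on 12 new against 3 resolved gives p = 0.035.

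**4. How much can be hidden?** This depends on the summary used.
- With zero net change in prevalence, new cases equal resolved cases, so they cannot exceed the number affected at baseline. At baseline prevalence 0, 10, 20 and 30% that is at most 0, 3, 6 and 9 of 30, or 0, 2, 4 and 7 of 22.
- With zero mean change this bound does not apply. One participant going from '6-7 days a week' to 'Not at all' (−4) offsets four going from 'Not at all' to '1 day a week' (+4). With n = 30 the mean change is 0.00 (SD 0.83), yet 4 of the 29 unaffected at baseline are new, although only one person was affected at baseline.

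**The case against.** Several points on the other side stand.

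- It would be too strong to say that the plan shows nothing but the net shift. The SD of change is promised, and an SD of 1.05 around a mean of 0.00 tells a reader that individual scores moved. It does not say how many people became symptomatic.
- A reader might infer that no side-effect count is planned anywhere. The documents do not support that. Protocol 5.5 lists side effects separately from physical symptoms, the SAP tables are broken, and the protocol refers to an attached item file. A separate side-effect item may exist. The checklist itself would still fall under the general change rule.
- A reader might infer that new symptoms would go unseen. Adverse events are reportable to the IRB (IRB application 9.10; Protocol 6.0), free-text items ask about other symptoms and about health that got worse, and interviews cover side effects. These can record individual cases. None has a planned rate, and interviewees are sampled on weight loss.
- The examples are constructed. If the diet pushes a symptom in one direction and few have it at baseline, the planned analysis will show a net rise and little is masked.
- A reader might take 4 of 24 as a side-effect rate of the diet. It is not one. People answering 'Not at all' at baseline sit at the floor of the scale and can only move up. With past-week recall and no control arm, some new reports will be background fluctuation, and four new beside four resolved is a pattern that fluctuation alone could give.

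**Conclusion.** The point holds as a gap in reporting. In the legible text, the only structured symptom checklist is analysed under a rule that nets new against resolved symptoms, and no count of new or worsened participants is promised. The lack of a stated chi-square/Fisher layout does not close the gap.

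The size of any masking is unknown. It requires participants who have the symptom at baseline and improve, and the plan gives no baseline rates. The 0/3/6/9-of-30 limit holds only for zero net change in prevalence. The conclusion also assumes that no illegible item already supplies the count.

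The documents do not show that harms are being concealed or that the primary outcomes are affected. This is worth considering, with medium confidence.

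**What to change.** In Protocol 5.6 and the SAP, add a baseline-by-follow-up table for each Physical Symptoms item at 6 and at 12 months, among participants with both surveys. From it report, with exact 95% CIs:

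- the number and percent worsened and improved by any category, side by side;
- the number and percent newly reporting the symptom among those answering 'Not at all' at baseline.

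Show survey non-returners separately. Rash has no rated item, so report it only as the number who volunteer it in free text.

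Label the results descriptive and uncontrolled. State that the new-onset group starts at the scale floor, so its count includes background fluctuation and is not a diet effect. State also that past-week items at 6 and 12 months miss early transient effects; IRB application 9.1 and Protocol 5.1 place diet side effects mainly in the first weeks.

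Cost: SAP wording and one supplementary table from data already collected. The table is not small: 24 items × 2 visits = 48 cross-tabulations, and three proportions from each make 144. Intervals will be wide, as the 5 to 37% above shows. The change does not recover early side effects and does not supply a control group.

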5.6 Data Analysis

Quantitative analysis

Descriptive statistics will be used for baseline survey response data including demographic and socioeconomic characteristics. For all continuous outcomes, we will calculate mean change and standard deviation from baseline to 6 months and 12 months and compare outcomes from baseline to 6 months and 12 months using paired *t*-tests. For all categorical outcomes, we will

use chi-square or Fisher's exact tests to examine changes from baseline to 6 and 12 months. All analyses will be conducted using Stata 14.

Qualitative analysis:

Semi-structured interviews will be recorded and transcribed verbatim. Interviews will then be imported into qualitative analysis software. Two investigators will independently read and code transcribed interviews. Interviews will then be coded jointly using consensus conferences. Interviews will be analyzed using directed content analysis²⁷, which is to say that codes will be created to reflect the main topics in the interview guide and to characterize the patterns and themes that emerged from the data.²⁸

